The primary aim of this pilot study is to examine whether an 8 week course of GCs in combination with rituximab is effective at inducing and maintaining disease remission through the 6-month timepoint in patients a subset of patients with AAV who have a more favorable prognosis.

III. Subject Selection

A. Inclusion and exclusion criteria

Inclusion criteria:

- Patients ages 18-85 years old
- Diagnosis of GPA or MPA according to the definitions of the Chapel Hill Consensus Conference
- New diagnosis or disease flare with a Birmingham Vasculitis Activity Score/Wegener's granulomatosis (BVAS/WG) of ≥ 3 .

Exclusion criteria:

- Renal disease in patients with PR3-ANCA as defined by any of the following:
 - Urinary red blood cell casts
 - Biopsy-proven glomerulonephritis
 - Increase in serum creatinine of $>30\%$ over baseline
- Severe renal disease in patients with MPO-ANCA as defined by both of the following:
 - Urinary red blood cell casts or biopsy-proven glomerulonephritis
 - Estimated glomerular filtration rate < 30 ml/min/1.73m²
- Diffuse alveolar hemorrhage requiring ventilatory support
- GC treatment for longer than 14 days prior to enrollment unless patient has been on a stable maintenance dose of prednisone at the time of the flare

- Daily oral cyclophosphamide within 1 month prior to enrollment
- Completed a remission induction course of cyclophosphamide or rituximab within 4 months of enrollment
- Current or past HBV infection (e.g., HBsAg positive, regardless of antibody status, HBsAg negative but anti-HBcAb positive).
- HIV infection
- History of anti-GBM disease
- Other uncontrolled disease, including drug and alcohol abuse, that may interfere with the study
- Pregnancy or breastfeeding
- History of severe allergic reactions to human or chimeric monoclonal antibodies

B. Source of subjects and recruitment methods

Subjects will be recruited via one of the following:

- New diagnosis or flare of previously diagnosed disease in patients followed in the Massachusetts General Hospital (MGH) Rheumatology or Nephrology Units.
- New diagnosis or flare of previously diagnosed disease in patients hospitalized at MGH.
- Referrals from subspecialty colleagues who are aware of our interest in AAV.

IV. Subject Enrollment

A. Methods of enrollment and procedures for obtaining informed consent.

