- Drs. [name], [name], [name] or [name] will discuss various treatment modalities with patients meeting the inclusion criteria. In addition to the study treatment protocol, the following treatment options will be discussed: Rituximab and conventional duration of GC therapy (6-12 months); cyclophosphamide and conventional duration of GCs, followed by azathioprine or methotrexate. Patients will be given adequate time to ask questions related to various treatment options and to discuss the study procedures in detail.
- Informed consent will be discussed with all potential study subjects by Drs. [name], [name], [name] or [name]. In addition to the physicians, a nurse or coordinator will be available to answer patient's questions.
- Patients will be given up to seven days to consider treatment options.

V. Study Procedures

A. Study visits and data collection

1. Screening visit
 - a. Diagnosis of new onset AAV or flare with BVAS/WG ≥ 3 will be confirmed by a complete history and physical examination performed by one of the investigators.
 - b. Treatment options will be discussed with the patient and informed consent for study participants will be obtained by one of the investigators.
 - c. The following laboratory values will be obtained – complete blood count (CBC), complete metabolic panel (CMP), erythrocyte sedimentation rate (ESR), C-reactive protein (CRP), ANCA, chronic hepatitis B infection panel, HIV antibody, B-cell flow cytometry, immunoglobulin levels (IgG, IgM and IgA), urinalysis and urine pregnancy test if applicable.
 - d. Imaging as deemed necessary by the investigator
 - e. Patients will begin GC therapy at a dose selected by the investigator or the treating physician with oral prednisone 60mg or 1mg/kg (if weight less than 60kg) or intravenous methylprednisolone, up to 1g/day for three days.
 - f. Patients will be started on omeprazole 20mg daily, trimethoprim-sulfamethoxazole one single strength tablet daily, calcium citrate 500mg twice daily and vitamin D 400 units twice daily.
 - g. Prior clinical assessment (labs) within one year can be used to determine screen eligibility.
2. Study visit 1 (no later than 14 days after the screening visit)
 - a. Treatment options will be discussed with the patient and informed consent for study participants will be obtained by one of the investigators.
 - i. All screening laboratory values must be completed

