 - a. Phone assessment for any new or ongoing symptoms performed by one of the physicians, research nurse or study coordinator
Prednisone decreased to 5mg if no new symptoms
 - b. Schedule urgent visit if new or worsening symptoms
10. Study visit 6 – eight weeks after first study visit
 - a. Patient assessed for partial disease remission defined as:
 - i. no new disease manifestations
 - ii. no worsening of existing disease
 - iii. BVAS/WG < 3
 - b. Adverse events assessed by one of the investigators

- c. Prednisone discontinued (or reduced to patient's stable chronic dose of prednisone in order to avoid adrenal insufficiency) if patient meets partial disease remission criteria Omeprazole discontinued
 - d. Laboratory tests – CBC, CMP, ESR, CRP, ANCA, urinalysis, B-cell flow cytometry
11. Phone call – nine weeks after first study visit
- a. Phone assessment for any new or ongoing symptoms performed by one of the physicians, research nurse or study coordinator Laboratory tests – CBC, CMP, ESR, CRP
 - b. Schedule urgent visit if new/worsening symptoms or worsening laboratories
12. Study visit 7– twelve weeks after first study visit
- a. Focused history and physical exam performed by one of the investigators
 - b. BVAS/WG assessed by one of the investigators
 - c. Adverse events assessed by one of the investigators
 - d. Laboratory tests – CBC, CMP, ESR, CRP, ANCA, urinalysis
13. Phone call – sixteen weeks after first study visit
- a. Phone assessment for any new or ongoing symptoms performed by one of the investigators
 - b. Laboratory tests – CBC, CMP, ESR, CRP, ANCA, and urinalysis
 - c. Schedule urgent visit if new/worsening symptoms or worsening laboratories
14. Study visit 8 – twenty weeks after first study visit
- a. Focused history and physical exam performed by one of the investigators
 - b. BVAS/WG assessed by one of the investigators
 - c. Adverse events assessed by one of the investigators
 - d. Laboratory tests – CBC, CMP, ESR, CRP, ANCA, urinalysis
15. Study visit 9 – twenty-four weeks after first study visit
- a. Focused history and physical exam performed by one of the investigators
 - b. BVAS/WG and VDI assessed by one of the investigators
 - c. Primary outcome measured - defined as BVAS/WG = 0 and prednisone dose = 0 (or maintained at patient's stable chronic dose of prednisone in order to avoid adrenal insufficiency) with no preceding flares.
 - d. Adverse events assessed by one of the investigators

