 - e. Laboratory tests – CBC, CMP, ESR, CRP, ANCA, urinalysis, B-cell flow cytometry, immunoglobulin levels (IgG, IgM and IgA).

Following the completion of six months on protocol, subjects will be treated according to the best medical judgment of their treating physician and will continued to be followed for six additional months.

16. Study visit 10 – 9 months after first study visit
 - a. Focused history and physical exam performed by one of the investigators
 - b. BVAS/WG assessed by one of the investigators
 - c. Adverse events assessed by one of the investigators
 - d. Laboratory tests – CBC, CMP, ESR, CRP, ANCA, urinalysis, B-cell flow cytometry
17. Study visit 11 – 12 months after first study visit
 - a. Focused history and physical exam performed by one of the investigators
 - b. BVAS/WG and VDI assessed by one of the investigators
 - c. Adverse events assessed by one of the investigators
 - d. Sustained remission assessed – defined as BVAS/WG = 0, prednisone dose = 0 (or maintained at patient’s stable chronic dose of prednisone in order to avoid adrenal insufficiency) and no disease flares during the study period.
 - e. Laboratory tests – CBC, CMP, ESR, CRP, ANCA, HACA, urinalysis, B-cell flow cytometry, immunoglobulin levels (IgG, IgM and IgA)

Additional visits may be required at the discretion of the investigator.

Missed visits

- If a subject is unable to attend a scheduled visit they may reschedule within 10 days of the time specified by the protocol.
- If a subject cannot attend a scheduled visit within 10 days of the date specified by the protocol a phone call and laboratory testing may be substituted on up to two occasions over the one year study period. The phone call will include a focused history and BVAS/WG scoring.

Mechanistic study

Subjects may be asked to give a blood sample for mechanistic studies, not to exceed 40ccs at the beginning of the study, at the 6 month timepoint, at the completion of the study and during disease flares.

Reimbursement

- Subjects will be given a \$40.00 echeck for each study visit.

Treatment of flares

Limited flares - having a new occurrence or worsening of one or more minor BVAS/WG items with a total BVAS/WG score < 3.

- First limited flare - prednisone increase up to 40 mg/day for one week followed by 4 week taper (30mg, 20mg, 10mg, 5 week per week). Lower starting

prednisone dose and shorter taper can be instituted at the discretion of the investigator.

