- Second limited flare - treatment according to best medical judgment of the investigator.

Severe flares – BVAS/WG ≥ 3 or experiencing one of the major BVAS/WG items.

- Patients with severe flares will be treated according to best medical judgment of the investigator.

Termination of protocol

The following pre-defined events will lead to subject's treatment according to best medical judgment:

- Two limited flares - defined as having a new occurrence or worsening of one or more minor BVAS/WG items.
- One severe flare - defined as BVAS/WG ≥ 3 or experiencing one of the major BVAS/WG items)
- Failing to achieve disease response at 4 weeks following the first rituximab infusion - defined as no new disease manifestations, no worsening of existing disease and stable or improved BVAS/WG score
- Failing to achieve partial remission at 8 weeks following the first rituximab infusion - defined as no new disease manifestations, no worsening of existing disease and BVAS/WG < 3 .

Subjects treated according to best medical judgment will continue to be followed according to a modified visit schedule of no less than once every three months for 12 months from study entry.

Data Collection

Data, including BVAS/WG scores, blood and urine test results, relevant radiology and pathology findings will be kept on data collection sheets and on Partners workstations or encrypted mobile devices using unique patient identifiers. Drs. [name], [name], [name], [name] as well as [name], [name], [name] and study staff will have access to coding sheets linking patient names and their unique identifiers. The data collection sheets will be kept in a locked file cabinet in the Rheumatology Unit.

Drs. [name] and [name] will review data on the number of subjects having limited or severe flares, achieving disease response, achieving partial remission and achieving remission after the first ten patients have been followed for six months. [name] will be responsible for determining whether the research should be altered or stopped.

PI's intention is to maintain the subject files electronically through utilizing a Redcap database as well as accessing additional information from LMR. The current Redcap

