- Grade 3 = Severe and undesirable adverse event
- Grade 4 = Life-threatening or disabling adverse event
- Grade 5 = Death

VI. Statistical Analysis

The following variables will be collected during the study:

- Baseline variables
 - o Age
 - o Sex
 - o Disease type (GPA or MPA)
 - o ANCA type
 - o New or relapsing disease
 - o If relapsing disease - treatment prior to flare
 - o BVAS/WG
 - o VDI
- BVAS/WG at visits 1 and 5-11
- VDI at visits 9 and 11
- Laboratory data at baseline and at visits 3, 5, 6, 7, 8, 9, 10 and 11 and after phone calls at 6,9 and 16 weeks of the study
 - o CBC
 - o CMP
 - o ESR
 - o CRP
 - o ANCA
 - o Urinalysis
 - o Flow cytometry for B-cells (measured at visits 1, 5, 9, 10, 11)
 - o HACA (measured at visits 1, 9, 11)
 - o Quantitative immunoglobulins (measured at visits 1, 9 and 11)
 - o Mechanistic studies (optional) (visit 1, 9, 11)
- Prednisone dose at each visit
- Adverse events

Study endpoints

Primary endpoint (assessed at 24 weeks) - Number of patients entering remission defined as BVAS/WG = 0 and prednisone dose = 0 (or maintained at patient's stable chronic dose of prednisone in order to avoid adrenal insufficiency).

Secondary endpoints (assessed at 24 weeks)

- Number of early treatment failures defined as patients who have new or worsening disease manifestations assessed at 4 weeks after study entry
- Number of severe flares defined as flare with BVAS/WG ≥ 3 or experiencing one of the major BVAS/WG items
- Number of limited flares defined as having a new occurrence or worsening of one or more minor BVAS/WG items
- Number of patients having a disease response
- Number of patients entering partial remission
- Number of patients entering sustained remission defined as BVAS/WG = 0, prednisone dose = 0 (or maintained at patient's stable chronic dose of prednisone in order to avoid adrenal insufficiency) and no disease flares during the study period.
- Area under the curve BVAS/WG

- Total GC dose

Statistical Methods

Continuous data will be summarized using descriptive statistics (e.g., mean, standard deviation, median, minimum, and maximum). Categorical data will be assessed using the Chi-square and the Fisher exact tests as appropriate. Descriptive statistics and two-sided 95% confidence intervals will be calculated to assist in the interpretation of efficacy outcomes.

Power Analysis

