- Infections are a concern with all drugs that affect the immune system. Rituximab has been associated with reactivation of hepatitis B virus and progressive multifocal leukoencephalopathy infection, in addition to other common viral and bacterial pathogens. Rituximab may decrease immunoglobulin levels. In the event of a severe infection immunoglobulins will be checked in order to determine whether the administration of intravenous immunoglobulin is indicated.
- Skin reactions, painful sores, ulcers, blisters and peeling skin (rare).
- Decreased white blood cell counts.

We anticipate that the risk of many of the infections which patients treated with the combination of rituximab and GCs are prone to will be attenuated by the shorter GC courses prescribed in this protocol.

There may be other risks of rituximab that are currently unknown.

VIII. Potential Benefits

Benefits to participating individuals

Individual patients may benefit from effective control of their disease with decreased toxicity from GC therapy.

Benefits to society

Results of this study may elucidate the optimal dose of GCs in the treatment of severe autoimmune disease such as AAV. Decreasing administration of GCs may decrease their side effects and thus decrease the cost burden on society associated with treatment of severe autoimmune disease.

IX. Monitoring and Quality Assurance

Drs. [name] and [name] will monitor study data to ensure the safety of patients. A formal compilation of safety and efficacy data will be performed after ten patients have been enrolled in the study and followed for six months.

Specific elements related to the safety of study subjects that will be examined include:

- Deaths
- Flares
- Failure to achieve disease response, partial remission or remission.
- Hospitalizations from any cause
- Infections
- Infusion reactions
- Status of peripheral B cell pool with regard to reconstitution
- Other unexpected and serious adverse events

Specific elements of efficacy that will be examined include:

- Decrease in disease activity as assessed by the BVAS/WG score
- Ability to discontinue GCs

The study will be terminated if 60% of subjects fail the primary endpoint. This includes patients who have one severe flare, two limited flares or discontinue the study medication due to an adverse event.

Adverse event reporting guidelines:

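### The three statements of the primary endpoint disagree, and none says how a non-flare failure of the 8-week course counts

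*Combined protocol and SAP*

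**What the plan says.** The aim in Section II is to learn whether an "8 week course of GCs in combination with rituximab is effective at inducing and maintaining disease remission through the 6-month timepoint".

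Primary success or failure is described in three places:

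- Section VI, Study endpoints: "Number of patients entering remission defined as BVAS/WG = 0 and prednisone dose = 0", or the stable chronic dose, assessed at 24 weeks. There is no condition on flares, on when prednisone stopped, or on other drugs.
- Section V.A, Study visit 9: the same two readings, but the sentence ends "in order to avoid adrenal insufficiency) with no preceding flares".
- Section IX: the study ends if 60% of subjects fail the primary endpoint. The text adds: "This includes patients who have one severe flare, two limited flares or discontinue the study medication due to an adverse event".

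Stopping prednisone at Study visit 6 (week 8) is conditional: it happens "if patient meets partial disease remission criteria". Under Termination of protocol, a patient leaves the protocol regimen for the physician's discretion after two limited flares, one severe flare, non-response at week 4, or "Failing to achieve partial remission at 8 weeks following the first rituximab infusion". Such patients stay in follow-up for 12 months from entry. Section I foresees that some patients will need glucocorticoids for more than two months.

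**The concern.** The trial asks whether eight weeks of glucocorticoid is enough. A patient who was not controlled at week 8 and needed more treatment is evidence that it was not. If that patient is later clear and off prednisone at week 24, Section VI records a success. The error can only run toward the tested regimen, and it acts on the primary result of a single-arm study, where no comparator would absorb it. The termination rule in Section IX uses the same endpoint, so it would react more slowly as well.

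**Working it through.** The plan has no figure to reproduce. The 20 patients are a convenience sample, with no target rate, alpha or power. The check is therefore mainly a comparison of texts, followed by arithmetic on assumed counts.

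**Step 1. Classify some possible patients.** All have BVAS/WG 0 and prednisone 0 at week 24.

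| Course before week 24 | Section VI | Visit 9 | Section IX |
|---|---|---|---|
| A. BVAS/WG 3 or more at week 8, nothing new or worse; longer prednisone or another agent | success | unclear | not clearly named |
| B. Stopped at week 8; one limited flare, treated with prednisone | success | failure | not named |
| C. One severe flare, then rescued | success | failure | failure |

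Patient C is caught outside Section VI. Patient B gets three different treatments. Patient A is the gap that no text closes.

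**Step 2. Is patient A a flare?** Termination of protocol words a severe flare as BVAS/WG of 3 or more, or a major item. Taken literally, a score of 4 at week 8 qualifies. Four features of the protocol go against that reading:

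- Entry itself requires a score of at least 3.
- At week 4, a stable score with nothing new or worse is a disease response and prednisone is lowered. Literally read, the same patient would be in severe flare.
- Week-8 failure is listed as an event apart from flares. Its score criterion would be redundant if any score of 3 or more were already a flare.
- The secondary endpoint in Section VI speaks of a flare that has such a score, not of the score alone.

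**Step 3. How much extra prednisone can a success hide?**

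- Patient A: 24 − 8 = 16, so almost 16 further weeks. The total is almost 24 weeks, about 24/8 = 3 times the tested course.
- Patient B: a first limited flare allows 1 + 4 = 5 weeks of prednisone, so any start up to week 24 − 5 = 19 is over by week 24. The scheduled taper from visit 1, at the 60 mg start, is 7 × (60×2 + 40×2 + 30 + 20 + 10 + 5) = 1,855 mg. The flare course at its maximum, reading its last step as 5 mg, is 7 × (40 + 30 + 20 + 10 + 5) = 735 mg, and 735/1,855 = 40% more.

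**Step 4. Effect on the rate.** One patient is 1/20 = 5 percentage points. Exact 95% limits are the 0.025 quantile of Beta(x, 21 − x) and the 0.975 quantile of Beta(x + 1, 20 − x). Suppose 14 of 20 are reported (an assumption):

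| Reported successes that had failed the course | Rate after reclassification | 95% CI |
|---|---|---|
| 0 | 14/20 = 70% | 46–88% |
| 1 | 13/20 = 65% | 41–85% |
| 2 | 12/20 = 60% | 36–81% |
| 4 | 10/20 = 50% | 27–73% |

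**Step 5. Effect on the termination rule.** Apply 60% at the review of the first ten patients, so at least 6 of 10 failures. P(X ≥ 6) is the sum over k = 6 to 10 of C(10,k) p^k (1 − p)^(10 − k). At p = 0.5 this is 386/1,024 = 0.38. The failure rates below are assumed:

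| True failure rate | All failures counted | 10 points missed | 20 points missed |
|---|---|---|---|
| 40% | 0.17 | 0.05 | 0.01 |
| 50% | 0.38 | 0.17 | 0.05 |
| 60% | 0.63 | 0.38 | 0.17 |

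**The case against.** The best defence is that the other texts already do most of the work. Visit 9 excludes any earlier flare. Section IX fails severe and repeated flares, and its list opens in a way that need not be exhaustive. Week-4 failure means new or worse disease or a rising score, which largely overlaps with the flare definitions. If the literal severe-flare wording is accepted too, nearly every termination event is a failure. A patient moved to the conventional 6 to 12 months of glucocorticoid (Section IV.A) would generally still be on prednisone at week 24 and would fail anyway. Early failures, response, partial remission, flares and total glucocorticoid dose are all reported as secondary endpoints, in a small pilot with no efficacy hypothesis test.

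Much of this stands, and it limits the width of the gap. It does not close it. The literal flare reading conflicts with the protocol's own response criteria, Section VI carries no flare condition whichever reading is chosen, and the secondary endpoints reclassify nobody. They also would not reveal other immunosuppressants: the only on-study drug variable that Section VI lists is prednisone dose.

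A reader might infer three stronger things that the documents do not support:

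- That rescued patients in general pass. After a severe flare or two limited flares, Visit 9 and Section IX both say otherwise.
- That a taper step held at a phone call lengthens the course unnoticed. Stopping at week 8 depends only on the partial-remission criteria, so the text does not show that a hold carries past week 8.
- That 12-month sustained remission has the same flaw. It is secondary, and after six months the protocol openly states that "subjects will be treated according to the best medical judgment of their treating physician".

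**Conclusion.** The concern holds in a limited form. The definitions in Section VI, Visit 9 and Section IX conflict, and none expressly covers failure of the 8-week course without a flare. Section VI, followed as written, counts such a patient as a success if the two week-24 readings are met, which does not answer the aim in Section II. Each case is worth 5 percentage points, in one direction. The termination rule loses sensitivity: with an assumed 50% true failure rate and 10 points missed, its chance of triggering at ten patients falls from 0.38 to 0.17.

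The documents give no frequency for these patients. Success also requires rescue, a score of 0 and full prednisone withdrawal within about 16 weeks, so the number may be small. All counts and failure rates used above are assumptions, as is applying the 60% rule at ten patients. The conflict between the texts rests on none of them.

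**What to change.** Write one primary definition and use it in Section VI, at Visit 9 and in Section IX. Keep the week-24 readings, and count as non-success any patient who before week 24:

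1. has any event listed under Termination of protocol, including week-4 or week-8 failure;
2. takes prednisone above the pre-entry chronic dose after the week-8 visit window; or
3. receives non-protocol immunosuppression for vasculitis.

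Reconcile the three texts on a single limited flare. Criterion 2 makes one treated with prednisone after week 8 a non-success, in line with Visit 9; a limited flare not treated that way still needs an explicit rule. State in the same place how an adverse-event stop counts, since only Section IX names it. Report the week-24 state regardless of treatment as a secondary result.

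This is an analysis definition and alters no treatment. Prednisone dose at each visit is already collected. The cost is revised wording and one concomitant-immunosuppressant field in the existing REDCap forms, with no extra visits or patients. The downside is that the reported remission rate may be lower.

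### Sections V and VI define two endpoints differently: the primary endpoint on whether an earlier flare counts as failure, and sustained remission on whether it is read at 24 weeks or 12 months

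*Combined protocol and SAP*

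**What the plan says.** **Primary endpoint.** Section V.A, item 15.c (visit 9, week 24) has three conditions: BVAS/WG of 0, prednisone at 0 or at the patient's stable chronic dose, and no flare beforehand. Section VI, Study endpoints, gives the primary endpoint at 24 weeks with the first two conditions only. Section IX ends the study if 60% of subjects fail the primary endpoint. It then says that failures include one severe flare, two limited flares, or stopping study medication for an adverse event.

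**Sustained remission.** Section VI places this item under the heading "Secondary endpoints (assessed at 24 weeks" and words it as "Number of patients entering sustained remission defined as BVAS/WG = 0, prednisone dose = 0", with the chronic-dose exception and freedom from flares over the study period. Section V.A, item 17.d (visit 11, 12 months) has "Sustained remission assessed" with the same components. The list for visit 9 does not mention it.

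**Length of the study.** The missed-visits rule allows phone calls to be "substituted on up to two occasions over the one year study period". Subjects who leave protocol treatment are followed on a "modified visit schedule of no less than once every three months for 12 months from study entry". After visit 9, "subjects will be treated according to the best medical judgment of their treating physician and will continued to be followed for six additional months".

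**The concern.** In an uncontrolled pilot of 20 patients the results are essentially counts of successes, so the definition of a success is the main thing the analysis section has to settle. Here two analysts working from the same data could report different primary counts, one following the visit schedule and the other Section VI. The same holds for sustained remission.

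The primary conflict matters more, because the 60% termination rule uses the same count. For sustained remission, a literal 24-week reading leaves out flares after week 24, although BVAS/WG is collected through visit 11. If the definitions are not fixed before the counts are made, the choice between them could be made with the results in view.

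**Working it through.** The documents give no figure to reproduce: N = 20 is a convenience sample, with no target rate or power calculation. The check is a comparison of the texts, followed by simple arithmetic for scale.

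**Step 1. How each text classifies particular patients for the primary endpoint.** All are at BVAS/WG 0 and prednisone 0 (or the stable chronic dose) at week 24.

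| Patient | Visit 9 (V.A) | Section VI | Section IX |
|---|---|---|---|
| No flare | success | success | not listed as failure |
| One limited flare, recovered | failure | success | not stated |
| One severe flare, recovered | failure | success | failure |

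The second row can occur. One limited flare does not end protocol treatment; under Termination of protocol, two limited flares or one severe flare do. The longest course described for a first limited flare is 1 + 4 = 5 weeks. A course started by week 24 − 5 = 19 can therefore be finished at week 24. The protocol also allows a shorter taper, so week 19 is an example and not a cut-off. The third row is less certain to be observed, because a patient with a severe flare moves to the modified schedule and a week-24 assessment is not assured.

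**Step 2. Size for the primary endpoint.** One patient is 1/20 = 5 points at full enrolment and 1/10 = 10 points at the ten-patient review. If the 60% rule is applied at that review (an assumption, since Section IX does not say when it applies), one such patient separates 5/10 = 50%, below the limit, from 6/10 = 60%, at the limit.

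**Step 3. The time point for sustained remission.**
- Section VI heading: 24 weeks.
- Visit 11: 12 months, about week 52, a flare-free window longer by 52 − 24 = 28 weeks.
- The flare clause in both places covers the study period, which the missed-visits rule puts at one year. A one-year condition cannot be completed at week 24.
- The heading is loose. Of the 8 items under it, 3 are earlier outcomes: early treatment failure ("new or worsening disease manifestations assessed at 4 weeks after study entry"), disease response (week 4) and partial remission (week 8).

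Twelve months is therefore the better-supported reading, but Section VI does not state it. A patient who is flare-free to week 24 and flares at month 9 is a success if the endpoint is closed at week 24 and a failure at visit 11.

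**Step 4. Size for sustained remission, illustrative only.** Assume 14/20 in flare-free remission at week 24, and that each later flare removes one success. Exact (Clopper-Pearson) two-sided 95% intervals:

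| Later flares | Rate | 95% CI |
|---|---|---|
| 0 | 14/20 = 70% | 45.7 to 88.1 |
| 1 | 13/20 = 65% | 40.8 to 84.6 |
| 2 | 12/20 = 60% | 36.1 to 80.9 |
| 4 | 10/20 = 50% | 27.2 to 72.8 |

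**The case against.** The strongest reply is that Section VI is coherent by itself: remission with or without an earlier flare is the primary endpoint, and flare-free remission is the secondary one. This stands in part. A reader might infer that 24-week sustained remission always repeats the primary endpoint and adds nothing. That is true only if the primary takes visit 9's wording; under Section VI's own wording the two differ. But keeping Section VI as written means setting aside both visit 9 and visit 11, so the texts still have to be reconciled.

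A second reply is that the study-period clause, read with the one-year study period, already makes a month 9 flare a failure, so only a loose heading is at fault. This is fair, and it is why 12 months is called the probable intent. It does not remove the need to say so in the analysis section.

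A reader might also see three competing definitions of the primary endpoint. The documents support two. Section IX says only what failure includes, which is not exhaustive and does not contradict visit 9 on a single limited flare; its gap is silence on that case.

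Finally, a reader might infer that treatment other than prednisone goes unrecorded after month 6, because "Prednisone dose at each visit" is the only post-baseline treatment variable listed in Section VI. The list does not show that: data are also entered from clinical notes into visit-specific forms that the documents do not reproduce.

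**Conclusion.** Both conflicts are real and should be corrected. The primary conflict carries more weight, because it changes who counts as a success in the main result and feeds the termination rule. The sustained-remission conflict concerns one secondary endpoint and is most likely a misplaced item under a loose heading.

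The firm figures are the steps per patient: 5 points at N = 20 and 10 points among ten patients. How many patients would be affected is unknown, because the documents give no expected flare or remission rate. The 14/20 starting point, the numbers of later flares and the use of the 60% rule at the ten-patient review are assumptions. Sample size and visit schedule are not affected.

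**What to change.** 1. In Section VI, add visit 9's condition of no earlier flare to the primary endpoint. This matches the aim in Section II, which is remission both induced and held to month 6. Report the count without the condition as a sensitivity result.
2. Reconcile Section IX with that text, so that the 60% rule refers to the same definition and the status of a single limited flare is clear.
3. Move sustained remission to a separate 12-month (visit 11) heading, and define the study period as baseline to month 12. If the sponsor did intend a 24-week version, name it as a separate endpoint.
4. Report flare counts for weeks 0 to 24, and separately for the later follow-up in months 6 to 12, so that flares behind 12-month failures are visible.
5. Describe the 12-month result as including treatment at the physician's judgment after month 6.

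The cost is wording only: BVAS/WG and prednisone dose are already collected through visit 11. Either rate may come out lower than under the more lenient reading.
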